2.2. Background

AD, often known as eczema, is a chronic, inflammatory skin disorder characterized by flaky skin lesions, intense pruritus, and a general deterioration in quality of life (QoL). AD flares occur at variable and unpredictable intervals. Patients with moderate AD may experience approximately 8 flares per year, each lasting approximately 14 days.³

Over the past 50 years, AD has become more prevalent, especially in industrialized, temperate countries such as the US.^{4, 5} AD is one of the most common, chronic, relapsing childhood dermatoses, impacting 15-30% of all children in the US and many have disease that persists into adulthood. Earlier reports indicated that, in up to 70% of cases, the disease greatly improved or resolved by late childhood, however more recent findings suggest that disease activity remains manifest for a prolonged period of time. Based on a total of

7157 patients enrolled in the Pediatric Eczema Elective Registry study, comprising a total of 22,550 person-years, it was concluded that symptoms associated with AD seem to persist well into the second decade of life and likely longer.⁶ The majority of studies conducted across multiple age groups suggest a continued decrease in prevalence with older age.⁷ Adult-onset AD does also occur, though it is less common. The prevalence of AD in adults is estimated to be 10%.⁸

Other treatment options for mild-to-moderate AD include regular use of emollients, topical corticosteroids (TCSs) of low-to-moderate potency, and topical calcineurin inhibitors (TCIs) (eg, pimecrolimus, tacrolimus) as a second line treatment. TCSs and TCIs have limitations for long term use due to safety concerns of TCS (striae rubrae, skin atrophy, telangiectasia, skin burning, erythema, and acneiform or rosacea-like eruptions) and TCI (inhibition of immune surveillance in the skin or systemically and warnings regarding potential for malignancies) adverse effects.^{9, 10} Additional treatments generally reserved for more severe AD include phototherapy (eg, ultraviolet (UV)-A light with or without psoralen, UV-B light narrowband or broadband) and systemic agents (eg, corticosteroids, cyclosporine, recombinant interferon- γ , mycophenolate mofetil, methotrexate, azathioprine, intravenous immunoglobulin and dupilumab).¹¹ Of the currently available therapies, none offers a long-term maintenance solution without long-term use safety concerns for mild-to-moderate AD.^{12, 13}

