4.2. Scientific Rationale for Study Design

This study will specifically evaluate if the crisaborole ointment, 2%, QD regimen is safe and efficacious for maintenance therapy and flare reduction during long-term treatment for 52 weeks. The primary and key secondary endpoints are based on the comparison of flare events between crisaborole and vehicle treatments.

The rationale for a QD regimen of crisaborole ointment, 2%, as a maintenance and flare reduction therapy is supported by the efficacy observed in a Phase 2 study (AN2728-AD-204). In Study AN27278-AD-204, crisaborole QD demonstrated that the efficacy onset of response was slower after 1, 2, and 3 weeks of treatment and did not show the same magnitude of AD signs and symptom improvement as BID at the end of 4 weeks of treatment. It was therefore considered that the BID regimen was more suitable for acute treatment of mild-to-moderate AD than the QD regimen. If a flare occurs during the double-blind maintenance period, then BID crisaborole will be provided as a rescue therapy for each flare episode. In the long-term open-label study (AN2728-AD-303) the median time to regain an ISGA score of clear or almost clear after AD relapse following no crisaborole treatment was 84 days. In this study each episode of flare will be treated with crisaborole BID for up to 12 weeks to ensure opportunity for participants to regain the treatment response status before resuming blinded QD maintenance treatment.

The long-term safety of crisaborole ointment, 2%, BID was demonstrated in an open-label extension study (AN2728-AD-303) where participants were treated with on-treatment and off-treatment cycles (corresponding to relapsing-remitting status of AD) for up to 52 weeks. In this study 7 and 8 participants received continuous crisaborole treatment for the entire 48 and 52 weeks, respectively. In this long-term study, no new clinically important safety signal was identified that had not already been identified in the short-term pivotal Phase 3 studies AN2728-AD-301 and AN2728-AD-302. It is therefore considered suitable to evaluate the long-term safety for 52 weeks in this study with crisaborole ointment, 2%, QD.

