8. STUDY ASSESSMENTS AND PROCEDURES

- Study procedures and their timing are summarized in the [SoA](#). Protocol waivers or exemptions are not allowed.
- Immediate safety concerns should be discussed with the sponsor immediately upon occurrence or awareness to determine if the participant should continue or discontinue study intervention.
- Adherence to the study design requirements, including those specified in the [SoA](#), is essential and required for study conduct.
- All screening evaluations must be completed and reviewed to confirm that potential participants meet all eligibility criteria. The investigator will maintain a screening log to record details of all participants screened and to confirm eligibility or record reasons for screening failure, as applicable.
- Procedures conducted as part of the participant's routine clinical management (eg, blood count) and obtained before signing of the consent/assent may be utilized for screening or baseline purposes provided the procedures met the protocol-specified criteria and were performed within the time frame defined in the [SoA](#).
- The maximum amount of blood collected from each participant by test parameter is summarized in [Appendix 2](#). Repeat or unscheduled samples may be taken for safety reasons or for technical issues with the samples.
- If blood collection is difficult for individual participants, venipuncture will be limited to 3 attempts, with additional attempts within 3–5 business days unless there is a medical emergency.
- For pediatric participants, low volume pediatric tubes will be used where possible and every effort should be made to ensure that blood volume collections do not exceed 1% of the total blood volume at any single time and 3% of the total blood volume during any period of 4 weeks.
- Urine pregnancy test using dipstick must be performed for all WOCBP ([Appendix 4](#)) during the study, if positive, a serum pregnancy test is required to confirm pregnancy ([Appendix 2](#)).
- All in-clinic visits, scheduled and unscheduled, will be conducted at study sites.
- Phone visits will occur at Days 141, 197, 253, and 309 (Weeks 20, 28, 36, and 44, respectively), and as a minimum, the participants should be assessed for any AE/SAE, concomitant medications/therapies, study treatment compliance, and any suspected flare (which will require an in-clinic visit for assessment).

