9.2. Sample Size Determination

A total of 162 events will provide approximately 96% power to detect a 1.8 ratio of median time of being flare-free (hazard ratio of 0.556) in the first QD period between crisaborole and vehicle at a significance level of 0.05 (2-sided, log-rank test). To get 162 events (first flare), approximately 250 participants who are eligible responders will be randomized (ratio=1:1) into the double-blind maintenance period of the study. When 162 events are observed, the randomization will be stopped even if less than 250 participants are randomized. On the other hand, if 250 participants are randomized, but 162 events cannot be reached, more participants will be randomized.

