9.4.1.2. Analysis Methods

Endpoint	Statistical Analysis Methods
Primary	
Primary Analysis
 
Time of flare-free maintenance in the first QD period up until the onset of the first flare during the 52-week maintenance period will be analyzed using a log-rank test, stratified by age group, duration of the BID treatment in open-label period, and ISGA score (clear [0], almost clear [1]) at randomization to test the difference between crisaborole QD versus vehicle QD. The proportion of participants maintaining flare-free at each month until the first flare onset in the maintenance period will be estimated by the product limit method; the median time of flare-free up until the first flare onset will also be estimated by this method. This analysis will be based on Estimand 1 using the Evaluable-DB population (see Section 9.1 and Section 9.3 for estimands and populations).
 
Sensitivity/Supplementary Analysis
 
For the above primary analysis, the flare is based on the investigator assessment of ISGA; time of flare is ISGA assessment time. Before investigator assessment, the flare may already have occurred. As a sensitivity analysis, flare is defined as participants reported AD worsening event. Analysis method and intercurrent events handling are the same as above for the primary analysis.
 
Another sensitivity analysis is interval censoring survival analysis. Time of flare is between the time of participants reported AD worsening and the time of investigator confirmed ISGA ≥ 2. This analysis will be based on Estimand 1 using the Evaluable-DB population.

Secondary	
Number of flare-free days will be analyzed using an analysis of covariance model, with treatment, age, duration of the BID treatment in open-label period, and ISGA score (clear [0], almost clear [1]) at randomization as factors. The number of flare-free days is total duration across the double-blind QD periods in the study for each participant. This analysis will be based on Estimand 2 using the Evaluable-DB population.

Endpoint	Statistical Analysis Methods

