6.1.1. Main Analysis

- Estimand strategy: Hypothetical ([Section 2.1.1](#)).
- Analysis Population: Evaluable-DB.
- Analysis method: Time-to-event analysis, Kaplan-Meier (product limit) method and log-rank test ([Section 5.2.4](#)).
- Intercurrent events: intercurrent events include discontinuation of treatment. If an intercurrent event (eg, death, dropout, loss to follow up, or end of study) occurs before the first flare, the duration of flare-free maintenance is the time from randomization to the first intercurrent event and is right censored. When a flare occurs first, the duration of flare-free maintenance is the time from randomization to the first flare and is not censored.

- Reporting results: At each month, the proportion of participants who had maintained flare-free status before the first flare, time-to-event curve, median (95% CI) time of maintaining flare-free, and number (%) of censored participants for each treatment group, and p-value from log-rank test will be presented.

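### Monthly flare-free proportions include four months with no scheduled ISGA (Weeks 20, 28, 36 and 44), where they may be overstated to the extent that flares go unreported

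*SAP*

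**What the plan says.** SAP 6.1.1 lists among the primary results: "At each month, the proportion of participants who had maintained flare-free status before the first flare, time-to-event curve". Protocol 9.4.1.2 agrees: "The proportion of participants maintaining flare-free at each month until the first flare onset in the maintenance period" is to be estimated by the product-limit method. The proportion flare-free by time point is part of the population-level summary of the primary estimand (SAP 2.1.1).

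The schedule of activities (protocol 1.3) places ISGA at in-clinic visits. Protocol 8 says: "Phone visits will occur at Days 141, 197, 253, and 309 (Weeks 20, 28, 36, and 44, respectively". Scheduled ISGA in the maintenance period therefore falls at Weeks 4, 8, 12, 16, 24, 32, 40, 48 and 52. SAP 6.1.2 confirms that the main analysis dates a flare at the assessment at which ISGA is 2 or more.

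There is also an unscheduled route. Participants or caregivers who suspect a flare are told to arrange a clinic visit promptly (protocol 4.1), and each phone visit asks about suspected flare and requires a clinic visit if there is one (protocol 8).

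**The concern.** Four of the 13 monthly estimates fall at weeks when the endpoint is not scheduled to be measured. A flare that starts after Week 16 and that nobody reports is counted as flare-free at Week 20 and enters the curve at Week 24. The table would treat these months like the others, and no planned output shows how many first flares were found only at a scheduled visit.

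The threshold makes silent flares plausible. ISGA 2 is mild disease, and protocol 9.4.1.2 accepts that a flare may precede its assessment. The two sensitivity analyses in SAP 6.1.2 do not close the gap, because both start from worsening that the participant reported. The second is called interval censoring, but its interval runs from report to confirmation and is then replaced by the midpoint. A flare that nobody reported has no such interval.

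At stake are the monthly proportions, the shape of the curve and the medians. The primary test is not.

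**Working it through.** **Plan's own figure.** Protocol 9.2: "A total of 162 events will provide approximately 96% power to detect a 1.8 ratio of median time", with hazard ratio 0.556 at two-sided 0.05. Schoenfeld: Φ(√162/2 × |ln 0.556| − 1.96) = Φ(3.736 − 1.960) = Φ(1.776) = 96.2%. It reproduces.

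**Hazards.** The documents state no monthly flare risk, so I assume constant hazards, no dropout, and 162 first flares among 250 participants (1:1) by Week 52. With S the vehicle flare-free proportion at Week 52:

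(1 − S) + (1 − S^0.556) = 2 × 162/250 = 1.296, so S = 0.246 on vehicle and 0.458 on crisaborole.

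Hazards: −ln(0.246)/52 = 0.0270 per week on vehicle; × 0.556 = 0.0150 on crisaborole. Medians (ln 2/hazard): 25.7 and 46.2 weeks.

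**Reported curve.** Let u be the share of flares that are silent, persist, and are found only at the next clinic visit; the rest are seen promptly. With c the latest clinic week up to t:

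reported S(t) = (1 − u)·S(t) + u·S(c), so the overstatement is u·[S(c) − S(t)].

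Week 20: vehicle u × (64.9 − 58.3) = 6.6u points; crisaborole u × (78.7 − 74.1) = 4.6u points. The documents do not give u, so the full range is shown (percentage points, vehicle / crisaborole):

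| Silent share u | Week 20 | Week 28 | Week 36 | Week 44 |
|---|---|---|---|---|
| 0 | 0 / 0 | 0 / 0 | 0 / 0 | 0 / 0 |
| 0.25 | 1.7 / 1.1 | 1.3 / 1.0 | 1.1 / 0.9 | 0.9 / 0.8 |
| 0.5 | 3.3 / 2.3 | 2.7 / 2.0 | 2.2 / 1.8 | 1.7 / 1.6 |
| 1 | 6.6 / 4.6 | 5.4 / 4.1 | 4.3 / 3.6 | 3.5 / 3.2 |

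At every clinic week the overstatement is 0 in this model.

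**Between-arm difference, Week 20.** True 15.8 points; 14.8 at u = 0.5; 13.7 at u = 1.

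**Medians read off the reported curves (weeks).**

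| u | Vehicle | Crisaborole | Ratio |
|---|---|---|---|
| 0 | 25.7 | 46.2 | 1.80 |
| 0.25 | 26.3 | 48 | 1.83 |
| 0.5 | 27.4 | 48 | 1.75 |
| 0.75 | 31.2 | 48 | 1.54 |
| 1 | 32 | 48 | 1.50 |

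**Log-rank test.** Simulation (600 runs per setting; u = 0, 0.5, 1) gave power of 96% to 97% and type I error of 4% to 7%, essentially the same under the planned schedule and a 4-weekly one. The simulation standard error at 5% is √(0.05 × 0.95/600) = 0.9 points.

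**Effect of the ±3-day window.** Take vehicle at Week 24, u = 0.5, visits spread evenly over the seven days. Read on the target day, 3/7 of visits are still to come: 0.5 × 3/7 × (64.9 − 52.3) = 2.7 points too high. Read at the end of the window, only silent flares since the visit (3 days earlier on average) are missed: 0.5 × 51.7% × 0.0270 × 3/7 = 0.3 points.

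**The case against.** The strongest reply is that the plan does look for flares between clinic visits. Beyond the unscheduled visits and the phone question, participants keep a body map on which they must record new lesions (protocol 8.1.4) and rate itch daily. The rows with u near 1 describe a trial in which none of this works. This stands: the bias is conditional, and its upper limit is not a forecast.

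Second, the bias is small beside sampling error. At Week 20 the standard error with 125 per arm is √(0.583 × 0.417/125) = 4.4 points on vehicle and √(0.741 × 0.259/125) = 3.9 on crisaborole. The bias also works slightly against crisaborole in the between-arm difference. Both are true, but the error is systematic, does not shrink with more participants, and can be avoided at little cost.

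Third, the monthly values are correct for time to confirmed flare, which is the event as dated. That is so, but the estimand speaks of onset and the output will be labelled flare-free.

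Stronger readings are tempting. A reader might infer that the four months are certainly overstated, or that the curve must flatten after Week 16 and mimic durable benefit. The first fails if flares are reported promptly. For the second, persistent flares all enter at the next clinic visit, and the curve is flat between visits only at u = 1. A lasting fall in apparent risk would need flares that clear unseen. The support for that is protocol 2.2: "Patients with moderate AD may experience approximately 8 flares per year, each lasting approximately 14 days". This is a general statement about moderate disease, and its rate of 8/52 = 0.154 per week is 5.7 and 10.3 times the design hazards of 0.0270 and 0.0150. Protocol 4.2 points the other way: "the median time to regain an ISGA score of clear or almost clear after AD relapse following no crisaborole treatment was 84 days", which is longer than the 56-day gap between visits.

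**Conclusion.** The point holds as a conditional one about reporting. The proportions at Weeks 20, 28, 36 and 44 may be overstated by an amount proportional to the share of flares that go unreported until the next clinic ISGA: at Week 20, from 0 to at most 6.6 points on vehicle and 4.6 on crisaborole, and about half of that if half are reported promptly. The medians can move, but their ratio runs from 1.50 to 1.83, so the documents do not support saying that the 1.8 design ratio would be understated. The primary comparison is sound, since both arms share the schedule.

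This rests on constant hazards, no dropout, persistent flares and the same silent share in both arms. With 10% or 30% yearly dropout, the vehicle median needed for 162 events in 250 falls to 23.7 or 19.7 weeks, and the overstatement would be somewhat larger. Clinic visits replaced by phone during the pandemic (protocol Appendix 9) are not modelled and would widen the gaps.

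**What to change.** 1. In SAP 6.1.1 and protocol 9.4.1.2, replace the monthly time points with the in-clinic ISGA weeks: 4, 8, 12, 16, 24, 32, 40, 48 and 52. Read each at the end of the schedule's ±3-day window (not the wider reporting windows of SAP Appendix 2). At Week 52, keep flare-free completers at risk until the window closes, so that the last value is not read from a shrinking risk set.
2. Do the same for maintenance of EASI response (SAP 6.3.1), which is also measured only in clinic.
3. Step 1 leaves the curve and medians unchanged. In SAP 6.1.2, therefore, set the interval in the interval-censoring analysis to run from the last ISGA below 2 to the first ISGA of 2 or more, and analyse it as interval-censored data instead of at a midpoint. Where the flare itself prompted the visit, onset probably lies late in the interval; say so when reporting.
4. Optional: tabulate by arm the first flares found at scheduled and at unscheduled visits.

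The cost is wording in two documents, four fewer tabulated time points and a little more programming. No visits or data are added, and the primary test does not change.

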6.1.2. Sensitivity/Supplementary Analysis

For the above main analysis, the definition of flare is based on the investigator assessment of ISGA, time of flare is the assessment time when ISGA \geq 2. In addition, a sensitivity analysis will be performed where flare definition includes an AD worsening event (preferred term= Dermatitis atopic or Eczema) reported by a participant prior to a confirmatory ISGA \geq 2. In this analysis, the time of onset of such event will be used as the onset of the flare. If a participant reported an AD worsening event but the investigator assessment is not a flare at the subsequent visit, this event is not a flare. Estimand strategy, analysis population, analysis method and intercurrent events handling are the same as above for the main analysis.

Another sensitivity analysis is interval censoring survival analysis. Time of flare is between the time of participants reported AD worsening and the time of investigator confirmed ISGA \geq 2. Because the exact flare time is not known, the midpoint of the above interval will be used as the flare time. Estimand strategy, analysis population, analysis method and intercurrent events handling are the same as above for the main analysis.

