8.3.6. Disease-Related Events and/or Disease-Related Outcomes Not Qualifying as AEs

The following disease related events are common in participants with AD:

- AD
- Eczema
- Flare of AD

Because these events are expected in this remitting and relapsing disease, they will not be reported as AEs. These events should be documented and recorded on the appropriate CRF as occurrence of a flare of AD during the maintenance period represents the efficacy outcome measure.

NOTE: However, if either of the following conditions applies, then the event must be recorded and reported as an AE:

- In the investigator's opinion, the event is of greater intensity or severity than the individual participant's condition at baseline (Day 1 of the run-in period).

OR

- The investigator considers that there is a reasonable possibility that the event was related to study intervention.

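### The sensitivity analyses of time to first flare date earlier onset from coded atopic dermatitis and eczema terms, which the protocol largely keeps out of adverse event reporting, so they may hardly test detection delay

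*SAP*

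**What the plan says.** Protocol 9.4.1.2 dates a flare at the ISGA assessment and gives the reason for two sensitivity analyses: "Before investigator assessment, the flare may already have occurred". In the protocol, the first analysis uses worsening of AD reported by the participant. It names no coded term and no AE source.

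SAP 6.1.2 narrows this. The earlier onset comes from "an AD worsening event (preferred term= Dermatitis atopic or Eczema) reported by a participant", and it counts only if an ISGA of 2 or more later confirms the flare. The second analysis, labelled interval censoring, runs from the reported worsening to the confirming ISGA visit, takes the midpoint and applies the main method. It does not repeat the preferred terms and names no other source. Neither paragraph says what happens to a confirmed flare with no reported worsening.

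Protocol 8.3.6 lists AD, eczema and flare of AD as disease-related events and states: "Because these events are expected in this remitting and relapsing disease, they will not be reported as AEs". They go on another CRF. There are two exceptions. One applies if, in the investigator's opinion, "the event is of greater intensity or severity than the individual participant's condition at baseline (Day 1 of the run-in period"). The other applies if a relationship to study intervention is reasonably possible.

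**The concern.** A preferred term is a field of coded event data, and the only coded events the SAP describes are AEs. SAP 6.2.2 also refers to AD worsening recorded as an AE. On that reading, the SAP looks for onset dates in the place where the protocol tells sites not to record them, apart from the exceptions.

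These are the only sensitivity analyses of the primary endpoint. Their purpose is to show whether the result depends on when flares reach an assessor. If participants on vehicle seek a visit sooner than those on crisaborole, ISGA dating alone favours crisaborole. An analysis with few earlier dates cannot reveal this, yet its agreement with the main result would be read as reassurance. The dates that do exist would belong to flares judged worse than baseline or possibly treatment-related, not to a representative set.

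**Working it through.** **1. The plan's own figure.** Protocol 9.2: "A total of 162 events will provide approximately 96% power", "hazard ratio of 0.556", two-sided alpha 0.05, 1:1 allocation. Schoenfeld: power = Φ(√(D/4) × |ln HR| − 1.96) = Φ(√40.5 × 0.587 − 1.96) = Φ(1.776) = 0.962. The Freedman variant gives 0.953. The stated 96% reproduces, and nothing below changes it.

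**2. When can a flare exceed run-in Day 1 on ISGA?** Entry is at ISGA 2 or 3 (Protocol 5.1). Randomisation requires ISGA 0 or 1 with an improvement of at least 2 grades (Protocol 4.1), and a flare is ISGA 2 or more. Anyone randomised at ISGA 1 therefore entered at 3.

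| Entry ISGA | Flare at 2 | Flare at 3 | Flare at 4 |
|---|---|---|---|
| 2 | not worse | worse | worse |
| 3 | not worse | not worse | worse |

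A flare at the threshold never exceeds Day 1 on this scale. The exception rests on the investigator's opinion of intensity or severity, so the table is a guide and not the rule itself. The documents give no distribution of flare grades, so no share of flares with an AE record can be derived.

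**3. What can move.** Both analyses keep ISGA confirmation, so the set of confirmed flares is fixed and only dates can change. With no earlier record, and assuming the ISGA date is then kept, nothing moves.

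**4. Size of the consequence.** The simulation used 125 participants per arm and exponential times calibrated to 162 flares among 250 participants in 52 weeks at the design HR. ISGA dates came from the clinic-visit schedule plus unscheduled visits, the log-rank test was unstratified, and there were 400 runs per setting.

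Assumptions: an unscheduled visit falls 1 to 14 days after onset; the mean lag is about 15 days; there is no dropout; flares without an earlier date keep the ISGA date. Unequal reporting means that 90% of vehicle and 10% of crisaborole participants call early. Entries are the mean absolute change in Z from the main analysis, for analysis 1 / midpoint analysis.

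| Flares with an earlier date | HR 0.556, equal reporting | HR 1, unequal | HR 0.75, unequal | Conclusion changes (HR 0.75, analysis 1) |
|---|---|---|---|---|
| 0% | 0 / 0 | 0 / 0 | 0 / 0 | 0% |
| 5% | 0.015 / 0.013 | 0.040 / 0.031 | 0.035 / 0.027 | 1.5% |
| 10% | 0.020 / 0.017 | 0.081 / 0.062 | 0.071 / 0.054 | 2.2% |
| 20% | 0.028 / 0.023 | 0.152 / 0.116 | 0.133 / 0.100 | 4.8% |
| 50% | 0.041 / 0.034 | 0.348 / 0.261 | 0.294 / 0.219 | 13.5% |
| 100% | 0.044 / 0.034 | 0.574 / 0.419 | 0.482 / 0.348 | 20.2% |

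Under equal reporting the shift is negligible even with full dating, so agreement there is correct and not a sign of a flaw. The loss appears under unequal reporting. At HR 1 with every flare dated, mean Z goes from −0.57 to 0.00 in analysis 1, so the detection bias is exposed. At HR 0.75 it goes from −2.43 to −1.95, or −2.08 by the midpoint. With 5% to 10% of flares dated, almost none of this is visible.

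**The case against.** The strongest reply is that SAP 6.1.2 never says AE. Protocol 8.3.6 requires these same events to be recorded on another CRF. If that form is coded, the preferred terms could come from it and the conflict would disappear. The AE source is an inference, although the documents name no other coded source.

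AE reporting is also not closed. The severity exception is a matter of opinion, and someone who entered at ISGA 2 and flares at 3 meets it on the scale itself. Protocol 8.1.4 leaves new lesions to medical judgement. Protocol 10.3.1 lists exacerbation of an existing condition as an AE, while exempting expected signs of the disease under study. Some dates will exist, and at a 50% share the analyses would move visibly under unequal reporting.

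A reader might infer four stronger things that the documents do not support:

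- **Both analyses reproduce the main result by construction.** This needs the AE source, the same source for the midpoint analysis, and a fallback to the ISGA date. None of these is written.
- **Nearly every flare lacks an earlier date.** No rate is given, so no count out of 162 can be stated.
- **Detection is routinely 8 weeks late.** Scheduled clinic visits are 8 weeks apart from Week 16 to Week 48. However, participants are told to call as soon as a flare is suspected, and the phone visits between ask about flares.
- **AE-dated flares differ by arm because application-site reactions were 5.6% versus 3.6%** (Protocol 2.3). Those figures come from earlier twice-daily studies and concern a different event.

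**Conclusion.** The concern holds in a limited form. On its natural reading, SAP 6.1.2 takes onset dates from records that Protocol 8.3.6 largely keeps from being created. Many flares will have no earlier date, and those that do are selected on severity or suspected relationship. The share is unknown.

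If undated flares keep the ISGA date, both analyses will stay close to the main result. With 5% to 20% of flares dated and reporting strongly unequal between arms, analysis 1 shifts Z by about 0.04 to 0.15, against about 0.5 to 0.6 with full dating. These sizes depend on the assumed calling pattern, lags and fallback.

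The primary test, its power and its Type I error are unaffected. What is weakened is the support that these analyses can lend to the primary result.

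**What to change.** In SAP 6.1.2:

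1. Drop the preferred-term restriction, in line with Protocol 9.4.1.2, and name one source of the worsening date for both analyses.
2. Take onset as the date the participant or caregiver first reported the suspected flare to the site, where that date is recorded. Protocol 4.1 asks for this contact, and Protocol 8 has phone visits ask about suspected flares.
3. Otherwise derive onset from PGIS/OGIS, which covers all ages (Protocol 8.1.6.4) and is collected daily (SAP 3.3.2). Pre-specify the size of worsening against the week before randomisation and the handling of missing days.
4. Keep the ISGA date when neither source gives an earlier one, and say so.
5. Report by arm how many flares have an onset before the ISGA visit.

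The cost is SAP wording and programming, provided the CRF holds the first-report date. The documents do not show that it does, so this must be confirmed first. Diary-derived onset is noisier than a dated report, and PGIS/OGIS was included as an anchor for the itch scales, so its use for onset should be labelled supportive.
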